9.10.3 Observational Endpoints

Observational endpoints will be summarized at all available time points at the time of analysis. These endpoints will be analyzed with standard statistical methods summarized in detail in the stand-alone statistical analysis plan that will be completed prior to formal analysis of the data. Standard statistical methods will be employed consistent with those summarized for the secondary endpoints. Statistical significance will be determined based on a two-sided p-value of 0.05. Only summary statistics (no p-values or 95% confidence intervals) will be provided in labelling upon agreement between Candesant and FDA. The p-values for the observational endpoints will not be adjusted for multiplicity and should be interpreted with caution.

- Baseline-adjusted mean improvement in QoL-7 instrument assessed by treatment group.
- Composite - proportion of patients with HDSS 1 or 2 AND 50% improvement in GSP assessed by treatment group.
- Composite - proportion of patients with HDSS 1 or 2 AND 75% improvement in GSP assessed by treatment group.
- Duration of efficacy: time from treatment to first observed reversion to HDSS 3 or 4 (a Kaplan-Meier analysis using median duration of efficacy will be compared between the treatment groups). Also performed for first reversion to subject's baseline HDSS.
- Mean change from baseline at 4 weeks in GSP by treatment group.

9.11 Specification of Subgroups for Analysis

The primary efficacy endpoint will be summarized within subgroups defined by Baseline HDSS, age, gender and race/ethnicity. Adverse events and local skin reactions will be summarized by Fitzpatrick Skin Types. It is important to note that the study is not powered to demonstrate statistical significance within subgroups and therefore it is not an expectation of the analysis that statistical significance be demonstrated with the subgroups.

CANDESANT BIOMEDICAL	CLINICAL STUDY PROTOCOL SAHARA STUDY	Document #: CB-CLP-001 Revision: E
-------------------------	---	---------------------------------------

10. ADVERSE EVENTS

10.1 Definitions

The definitions below are in accordance with ISO 14155. Both the investigator and the sponsor will comply with all local medical device reporting requirements.

Adverse Events (AEs) may occur during the investigational procedure or during the follow-up phase. AEs occurring prior to the use of the N-SWEAT device will be documented in the subject's medical record but will not count as related to the investigational device or procedure.

10.1.1 Adverse Events

An AE is defined as any untoward medical occurrence, unintended disease or injury, or untoward clinical signs (including abnormal laboratory finding) in study participants, users, or other persons, whether or not related to the investigational medical device. This definition includes events related to the investigational medical device and events related to the procedures involved except for events in users or other persons, which only include events related to investigational devices.

10.1.2 Adverse Device Events

An Adverse Device Event (ADE) is defined as an AE related to the use of an investigational medical device. This definition includes any adverse events resulting from insufficient or inadequate instructions for use, deployment, implantation, installation, or operation, or any malfunction of the investigational medical device as well as any event resulting from use error or from intentional misuse of the investigational medical device.

10.1.2.1 Treatment-Related Adverse Event

A treatment-related AE is any AE that starts on or after the time of treatment that a physician considers a result of treatment; the AE may or may not be related to the study device. Treatment-related events will be assessed for relationship to the device. The occurrence of treatment-related AEs will be summarized as part of the assessment for safety.

10.1.3 Serious Adverse Events

A Serious Adverse Event (SAE) is an AE that:

- Led to death.
- Led to serious deterioration in the health of the participant, that either resulted in:
 - A life-threatening illness or injury. The term *life-threatening* in the definition of *serious* refers to an event in which the participant was at risk of death at the time of the event. It does not refer to an event that hypothetically might have caused death if it were more severe.
 - A permanent impairment of a body structure or a body function

CANDESANT BIOMEDICAL	CLINICAL STUDY PROTOCOL SAHARA STUDY	Document #: CB-CLP-001 Revision: E
-------------------------	---	---------------------------------------

- Inpatient or prolonged hospitalization. Planned hospitalization for a pre-existing condition, or a procedure required by the protocol, without serious deterioration in health, is not considered an SAE.
- Medical or surgical intervention to prevent life-threatening illness or injury or permanent impairment to a body structure or a body function.
- Led to fetal distress, fetal death, or a congenital abnormality or birth defect.

If an event is not an AE per the definition above, then it cannot be an SAE even if serious conditions are met (e.g., hospitalization for signs/symptoms of the disease under study, death due to progression of disease).

10.1.4 Serious Adverse Device Events

A Serious Adverse Device Event (SADE) is defined as an ADE that has resulted in any of the consequences characteristic of an SAE.

10.1.5 Device Deficiency

A device deficiency is an inadequacy of a medical device with respect to its identity, quality, durability, reliability, safety, or performance. Device deficiencies include malfunctions, use errors, and inadequate labeling.

10.1.6 Unanticipated Adverse Device Events

According to 21 CFR 812.3(s), a Unanticipated Adverse Device Event (UADE) is any serious adverse effect on health or safety or any life-threatening problem or death caused by, or associated with, a device, if that effect, problem, or death was not previously identified in nature, severity, or degree of incidence in the investigational plan or application (including a supplementary plan or application), or any other unanticipated serious problem associated with a device that relates to the rights, safety, or welfare of subjects.

10.2 Adverse Event Review by Investigator

Each AE will be assessed by the investigator as to its relationship and level of relatedness to the device and/or procedure. In addition, the investigator will identify the date of onset, any required treatment or intervention, severity, and duration. All AEs will be monitored until they are adequately resolved, stabilized and/or explained.

10.2.1 Severity

The investigator will use the terms below to rate the severity of each AE.

Note that an event is defined as serious when it meets at least one of the predefined outcomes as described in the definition of an SAE, NOT when it is rated as severe per the table below.

Table 6. AE Severity

Severity	Description
Mild	Awareness of signs or symptoms, but easily tolerated and are of minor irritant type causing no loss of time from normal activities. Symptoms do not require therapy or a medical evaluation; signs and symptoms are transient.
Moderate	Events introduce a low level of inconvenience or concern to the participant and may interfere with daily activities, but are usually improved by simple therapeutic measures; moderate experiences may cause some interference with functioning
Severe*	Events interrupt the participant's normal daily activities and generally require systemic drug therapy or other treatment; they are usually incapacitating

Based on the National Institute on Aging (NIA) Adverse Event and Serious Adverse Event Guidelines (2018)

**Severe does not indicate an SAE (Serious Adverse Event). Please see 10.1.3 for a definition of Serious Adverse Event.*

10.2.2 Relationship to N-SWEAT Patch

The investigator will use the terms below to rate the relationship of the AE to the patch.

Table 7. AE Relationship to Device

Relationship	Description
Not Related	
 • not associated with patch • due to an underlying or concurrent illness or effect of another device or drug
Unlikely	
 • little or no temporal relationship to the patch • a more likely alternative etiology exists
Possible	
 • temporal sequence between patch and event • is such that the relationship is not unlikely or • Subject's condition or concomitant therapy could have caused the AE
Probable	
 • temporal sequence is relevant or • event abates upon patch application completion/removal or • event cannot be reasonably explained by the Subject's condition
Highly Probable	
 • temporal sequence is relevant and • event abates upon patch application completion/removal or reappearance of the event on repeat patch application

10.3 Adverse Event Reporting

All AEs and ADEs will be recorded by the investigator or designee on the case report forms (CRFs) provided. The investigator at each site is ultimately responsible for reporting AEs to the IRB according to IRB requirements and to the sponsor in accordance with the Investigational Plan and applicable FDA regulations. The site will be instructed to report all AEs considered moderate or severe and all local skin reactions to Candesant within 5 working days of the identification of the AE.

If an Adverse Event is considered a local skin reaction within the treated area, photos are required to be submitted as part of the Adverse Event Report. Submitted photos should show documentation of AE onset, AE progression and/or healing and AE

CANDESANT BIOMEDICAL	CLINICAL STUDY PROTOCOL SAHARA STUDY	Document #: CB-CLP-001 Revision: E
-------------------------	---	---------------------------------------

resolution (if applicable). Photos are to be taken with a high-resolution camera with the arm in the standardized treatment position and adequately illuminated. Photos are to be marked with Subject ID, date and subject side (i.e. Right or Left). Photos are to be taken with a measurement calibration reference visible.

AEs or complications meeting the definition for UADEs must be reported by the investigator to the sponsor as soon as possible, but in no event, later than 10 working days after the investigator first learns of the event. The sponsor will conduct an evaluation of any reported UADEs and will report the results of this evaluation to the FDA, IRBs, and participating investigators within 10 working days after first receiving notice of the event.

Descriptive and photographic data will be recorded and maintained on file for all AEs regardless of severity or device-relatedness. All observed local skin reactions will also be recorded.

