11.5 Safety-Related Stopping Rules

The study sponsor will be charged with monitoring the study for safety and for auditing the quality of the data. Stopping rules will be activated if there are any perceived safety concerns related to the N-SWEAT Patch as demonstrated by the occurrence of any of the following:

FIRST 10 SUBJECTS

1. One report of a Serious Adverse Event due to:
 - thermal or caustic injury
 - blister
 - erosion
 - pustule
 - erythema lasting > 7 days or developing >7 days after the treatment
 - infection
 - suspected infection of the skin or soft tissue in the axilla

AFTER 10 SUBJECTS

1. If 10% of N-SWEAT treated subjects have a reported severe device-related Adverse Event as defined in Table 6, or
2. If the DSMB recommends stopping due to a safety signal as described in section 10.4.

Should a stopping rule be triggered:

1. Enrollment and treatment will be suspended and a root cause investigation into all involved AEs will be conducted within 5 days by an independent Data Safety Monitoring Board to determine the cause of the event(s), to look at any trends and to evaluate potential safety issues.

CANDESANT BIOMEDICAL	CLINICAL STUDY PROTOCOL SAHARA STUDY	Document #: CB-CLP-001 Revision: E
---------------------------------	---	---------------------------------------

2. A full report (including photos, description, onset, duration, severity, causality, intervention, and sequalae) will be sent to FDA no later than 5 working days after DSMB review is complete.
3. Candesant will work with FDA, DSMB and study investigators to establish a process to re-start the study.

CANDESANT BIOMEDICAL	CLINICAL STUDY PROTOCOL SAHARA STUDY	Document #: CB-CLP-001 Revision: E
-------------------------	---	---------------------------------------

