13.4 Investigator Reports

The investigator(s) will be responsible for reporting per 21 CFR 812.150(a) and according to applicable IRB requirements and GCP: Consolidated Guidance. Reports must identify subjects using the unique identifier to protect confidentiality.

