13.6 Other Investigator Reports

The investigator for each study center is responsible for submission of reports to the sponsor according to the schedule shown below. All reporting timelines are “within knowledge of the occurrence.” Reports must identify subjects using the study’s unique identifier to protect subject’s confidentiality.

Type of Notification	Time Constraints
Withdrawal of IRB Approval	verbal report within 24 hours followed by a written report within 5 working days
Informed Consent NOT Obtained	verbal or written report within 5 working days

CANDESANT BIOMEDICAL	CLINICAL STUDY PROTOCOL SAHARA STUDY	Document #: CB-CLP-001 Revision: E
---------------------------------	---	---------------------------------------

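### Protocol 10.3 sets no SAE reporting deadline and two unreconciled limits for UADEs, so the 11.5 stopping rules can act about a week after the triggering event is identified

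*Protocol*

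**What the plan says.** Protocol 10.3 contains two numeric limits for site-to-sponsor reporting. Sites are to "report all AEs considered moderate or severe and all local skin reactions to Candesant within 5 working days of the identification of the AE". For UADEs, which 10.1.6 defines by serious harm or a serious problem, the report is due as soon as possible and no "later than 10 working days after the investigator first learns of the event".

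No line gives a number of days for SAEs as a class. Section 10.3 refers generally to the Investigational Plan and FDA regulations, and 13.4 adds: "The investigator(s) will be responsible for reporting per 21 CFR 812.150(a) and according to applicable IRB requirements". The table in 13.6 covers two other matters. Withdrawal of IRB approval needs a "verbal report within 24 hours followed by a written report within 5 working days", and missing consent has 5 working days.

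Section 11.5 then builds stopping rules on reported events. For the first 10 subjects the trigger is "One report of a Serious Adverse Event due to" one of a closed list of causes: burn or caustic injury, blister, erosion, pustule, prolonged or late erythema, and infection. After 10 subjects, the triggers are a reported severe device-related event in 10% of N-SWEAT subjects, or a DSMB recommendation. A trigger halts enrollment and treatment.

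**The concern.** A stopping rule protects the next subject only from the moment the sponsor hears of the event. The protocol asks for speed elsewhere: the synopsis and 8.8 call for a visit or telehealth contact within 24 hours of treatment-site symptoms, and 11.5 wants the DSMB root-cause investigation within 5 days of a trigger. Yet the step that connects the two, site to sponsor, may take 5 working days.

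The limits also do not line up with seriousness. The category that is serious by definition carries the longer outer limit, and SAEs have no limit of their own. Section 10.2.1 states that severity and seriousness are different, so the severity-based 5-day rule is not an SAE rule. A UADE that is also moderate, severe or a skin reaction falls under both limits, with no statement of precedence. At stake is how many more people are treated before a halt that the plan itself requires.

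**Working it through.** The plan gives no figure for this lag, so there is none to reproduce. The check has two parts.

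**Which limit applies to which event**

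| Event | Limit to sponsor | Place in protocol |
|---|---|---|
| Any local skin reaction | 5 working days | 10.3 |
| Moderate or severe AE | 5 working days | 10.3 |
| UADE | As soon as possible, at most 10 working days | 10.3 |
| UADE that is also moderate, severe or a skin reaction | Both; precedence not stated | 10.3 |
| SAE as a class | No number of days | 10.3, 13.4, 13.6 |

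Most causes listed in 11.5 are treatment-site skin findings. Appendix B names erythema, pustule and erosion, and covers blisters as vesicles or bullae. Burn or caustic injury and infection are not named there, but would be due in 5 working days if graded moderate or severe. The only SAE outside both limits is one graded mild that is neither a skin reaction nor a UADE. Table 6 reserves mild for transient events needing no therapy or medical evaluation, so such an SAE is unlikely.

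**How many subjects are treated during the lag**

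Inputs from the synopsis:
- Roll-in: 10 subjects at 1 site in 1.5 months, all on the active patch.
- Randomized: up to 110 subjects at up to 14 sites in 3 months, 1:1.

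Assumptions: even accrual, the full reporting allowance used, and 365.25/12 × 5/7 = 21.74 working days per month. Expected further subjects = accrual per working day × lag.

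1. Roll-in rate: 10/(1.5 × 21.74) = 0.307 per working day.
   - 5 working days: 0.307 × 5 = 1.5 subjects.
   - 10 working days: 0.307 × 10 = 3.1 subjects.
2. With Poisson accrual, the chance of at least one further roll-in subject in 5 working days is 1 − exp(−1.53) = 0.78. The chance of three or more is 0.20.
3. If roll-in took 1 to 2 months instead (an assumption), the ranges are 2.3 down to 1.2 subjects at 5 working days, and 4.6 down to 2.3 at 10. The cap of 10 subjects lowers all of these for events late in the cohort.
4. Randomized rate: 110/(3 × 21.74) = 1.69 per working day. At 5 working days: 8.4 subjects, about 4.2 on N-SWEAT. With 100 randomized instead of 110: 7.7 and 3.8.
5. With a lag of one working day: 0.3 roll-in subjects, or 1.7 randomized (0.8 on N-SWEAT).

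**The case against.** The strongest reply is that the gap is mostly one of labelling. Nearly every SAE from the 11.5 causes is already due in 5 working days, because it is a skin reaction or is moderate or severe. The UADE limit is qualified by a duty to report as soon as possible, and nothing exempts a UADE from the 5-day rule. Most of the listed causes are also anticipated risks in 11.2, so they would be UADEs only if unexpected in severity or incidence. The roll-in runs at one site, so the site that sees the event is the only one treating. Section 15.1 lets the investigator as well as the sponsor discontinue the study, and section 5 has randomization wait for review of the roll-in safety data.

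Much of this stands, and it rules out three stronger readings that a reader might infer:

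- *Deadlines run opposite to seriousness.* They do not do so cleanly. The 10 days are an outer bound, and for most such events the 5-day rule applies as well.
- *SAEs have no deadline at all.* This is true of the class but not of most SAEs that matter here. Their absence from 13.6 is no defect in itself, since that table is for other notifications.
- *One SAE could be followed by 8 to 17 more randomized subjects before the rule acts.* The one-SAE rule covers only the first 10 subjects. The count of 17 (1.69 × 10) also needs the full 10-day limit, whereas the 10% rule counts severe events, which are due in 5 working days.

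The objection does not remove the 5-working-day lag. The documents do not say that the roll-in site would pause on its own. In the randomized cohort, no single site among up to 14 can see that 10% of N-SWEAT subjects have been affected; only pooled reports show it.

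**Conclusion.** The point holds as a gap in reporting speed and clarity. Suspension under 11.5 can follow the identification of a triggering event by about a week with every site in full compliance. The size is about 1 to 2 further roll-in subjects under the one-SAE rule, and about 8 randomized subjects, half on N-SWEAT, under the 10% rule. About 3 roll-in subjects is the figure only if the 10-day UADE limit governed.

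The reading of the text is firm. The counts are less so: they rest on planned, even accrual and on sites using the whole allowance, and a site that reports or pauses sooner would bring them down. The text of the cited regulation was not available, so any SAE deadline that it adds is not counted. The efficacy analysis and the sample size are unaffected. This should be changed, but it does not undermine the trial.

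**What to change.** In Protocol 10.3:

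- Require sites to notify the sponsor within 24 hours (one working day) of becoming aware of any SAE, any suspected UADE, and any event that could count toward an 11.5 trigger. The written form and photographs follow.
- State that the shorter limit governs where two apply.
- Keep 5 working days for the other moderate or severe events and skin reactions.

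No figure in the documents dictates 24 hours. It is a judgement, in line with the 24-hour contact that the protocol already expects for treatment-site symptoms and the verbal report it requires for loss of IRB approval. The cost is protocol and site-training wording and slightly faster reporting of a few events. The stopping rules themselves, treatment, endpoints and analysis are unchanged.

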10.4 Independent Adverse Event Review

An independent Data Safety Monitoring Board (DSMB) will be established to protect patient safety and ensure data integrity for the Sahara Study. The board will be comprised of 3-5 clinical physicians with expertise in dermatology who are not participants in the study. The DSMB will serve in three roles in the safety overview of the Sahara study:

- To convene as needed for review of Adverse Events related to stopping rules and to determine a root cause analysis of these events.
- To conduct a monthly blinded review of all AEs reported during enrollment and until the final subject has reported for 4-week follow-up.
- If warranted, to request unblinding and fully investigate any potential safety signal. This investigation may result in a recommendation to stop the clinical study if the findings indicate an unacceptable or unknown safety risk.

A charter will establish the DSMB details on the operation of the DSMB.

CANDESANT BIOMEDICAL	CLINICAL STUDY PROTOCOL SAHARA STUDY	Document #: CB-CLP-001 Revision: E
-------------------------	---	---------------------------------------

11. RISK-BENEFIT ASSESSMENT

11.1 Potential Benefits

It is expected that the Candesant Biomedical N-SWEAT Patch may provide some benefit to the subject by reducing the amount of sweat that they produce after treatment. This sweat reduction would be expected to offer a quality of life improvement to the subject. The true benefits are not fully known but will be assessed and measured during this study. It is possible that there is no benefit to the N-SWEAT Patch.

Since this a randomized study with a sham control, the subjects who receive the sham patch are not expected to have any immediate benefit in the reduction of sweating with their participation. However, their participation may be beneficial in the future in helping to assess the potential of having this technology available to all patients with excessive sweating or primary hyperhidrosis.

11.2 Potential Risks

The identified potential risks to the study subject that may be associated with treatment for excessive sweating or hyperhidrosis of the axilla are shown below. The risks of these events occurring for subjects treated during the Sahara Study have been mitigated as much as possible by device design and training

- Allergic reaction to device materials
- Blister formation
- Burning or stinging
- Decreased hair growth
- Discomfort / Pain
- Discomfort during post-treatment cleaning
- Infection
- Injury to eyes or mouth, if gloves or hands that handled the device touch
- Intolerance of deodorant
- Irritation
- Itching, tightness, tingling
- Numbness or altered sensation
- Redness (erythema), blotchiness, bumps
- Scar or contracture
- Skin corrosion
- Skin discoloration
- Skin erosion
- Sweating in other parts of the body
- Swelling (edema) or bruising
- Thermal Injury

